14.5. Primary Analysis

LogMAR Visual Acuity

Binocular, high luminance, high contrast visual performance on logMAR scale will be analyzed using a linear mixed model. Each regression model will include the experimental design factors: distance as fixed effects. Other baseline characteristics known of importance such as age, gender, and/or add power will be included as fixed covariates when appropriate. Subject nested in site will be included as random covariates when appropriate. The covariance between residual errors from the same subject across different charts will be selected based on the finite-sample corrected Akaike's Information Criterion.⁶ Covariance structures considered may include: Homogenous compound symmetry (CS) and Unstructured covariance structure (UN). The structure that returns the lowest Akaike Information Criteria Corrected (AICC) will be selected as the structure that best fit the data.

Comparisons will be carried out using 95% confidence intervals constructed of least-square means (LSM) from the linear mixed models. Statistically superiority will be concluded if the upper limits of the confidence intervals are below the thresholds for corresponding distances.

CLUE Vision Scores

CLUE vision scores will be analyzed using a linear mixed model adjusting for baseline values as fixed covariate. The model will include the experimental design factors: time (6-8 day or 12-16 day) as fixed effects. Other baseline characteristics known of importance such as age, gender, and/or add power will be included as fixed covariates when appropriate. The covariance between residual errors from the same subject across different time will be selected based on the finite-sample corrected Akaike's Information Criterion.⁶ Covariance structures considered may include: Homogenous compound symmetry (CS) and Unstructured covariance structure (UN). The structure that returns the lowest Akaike Information Criteria Corrected (AICC) will be selected as the structure that best fit the data.

Comparisons will be carried out using 95% confidence intervals constructed of least-square means (LSM) from the linear mixed models for each time. Statistically superiority will be concluded if the lower limit of the confidence interval is greater than 32 points.

In all models, the Kenward and Roger method⁷ will be used for the calculation of the denominator of degrees of freedom.

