2.3. Hypotheses

The following hypotheses will be tested throughout this investigation.

Primary Hypotheses

1. After 12-16 days of wear, the binocular bright, high contrast distance (4M) logMAR visual acuity of the test lens will be statistically better than +0.1 logMAR. This will be determined using ETDRS LogMAR acuity testing charts.
2. After 12-16 days of wear, the binocular bright, high contrast near (40cm) logMAR visual acuity of the test lens will be statistically better than +0.17 logMAR. This will be determined using Guillon/Poling LogMAR acuity testing charts.
3. After 12-16 days of wear, the PRO CLUE vision score for the test lenses will be statistically better than 32 points. This will be recorded by the subject using the CLUE follow-up questionnaire.

Secondary Hypotheses
Not applicable.

Other Hypotheses
Not applicable.

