7. STUDY EVALUATIONS

7.1. Time and Event Schedule

Table 3: Time and Events

Visit Information	Visit 1 Screening, Baseline, Treatment 1	Visit 2 Treatment 1 Follow-up	Visit 3 Treatment 1 Follow-up, Treatment 2
Time Point	Day 1 (Day 0)	Day 7 ± 1 From Visit 1	Day 7 ± 1 from Visit 2
Estimated Visit Duration	2.5 hours	1.0 hours	1.5 hours
Statement of Informed Consent	x		
Demographics	x		
Medical History/Concomitant Medications/Review	x	x	x
Current Habitual Correction	x		
Habitual Contact Lens Information (if applicable)	x		
Contact Lens History (if applicable)	x		
Habitual Lens Wear Time (if applicable)	x		
Screening Inclusion/Exclusion Criteria	x		
Ocular Symptoms	x	x	x
Entrance Distance and near Visual Acuity	x	x	x
Lens Removal (if applicable)	x	x	x
Keratometry	x		
Subjective Sphero-Cylindrical Refraction	x		
Near Add Determination	x		
Ocular Dominance	x		
Add Refinement	x		
Near Visual Acuity	x		
Slit Lamp Biomicroscopy	x	x	x
Baseline Inclusion/	x		

Visit Information	Visit 1 Screening, Baseline, Treatment 1	Visit 2 Treatment 1 Follow-up	Visit 3 Treatment 1 Follow-up, Treatment 2
Time Point	Day 1 (Day 0)	Day 7 ± 1 From Visit 1	Day 7 ± 1 from Visit 2
Estimated Visit Duration	2.5 hours	1.0 hours	1.5 hours
Exclusion			
Lens Selection	X	X (if optimized)	
Right Lens Insertion	X	X (if optimized)	
Right Lens 1 Minute and 3 Minute Rotation	X	X (if optimized)	
Left Lens Insertion	X	X (if optimized)	
Left Lens 1 Minute and 3 Minute Rotation	X	X (if optimized)	
Lens Settling	X	X (if optimized)	
Toric Fit Assessment	X	X	X
Subjective Lens Fit Assessment	X	X	X
Visual Satisfaction	X	X (if optimized)	
Subjective Acceptance		X	X
Study Lens Distance and Near Visual Acuity	X	X	X
Over Refraction and Visual Acuity	X	X	
Lens Power Modification (if applicable)	X		
Insertion and Removal Training	X		
Determination of Successful I/R	X		
Determination of Lens Optimization		X	
Lens Optimization (if required)		X	
Insertion of Study Lenses	X	X	
Post Fit Questionnaires	X	X	
Exit Snellen Distance and Near Visual Acuity	X	X	
Dispensing Criteria	X	X	
Subject Instructions	X	X	
Instruction Guide	X		
Lens Dispensing	X	X	
Schedule Follow-Up	X	X	

Visit Information	Visit 1 Screening, Baseline, Treatment 1	Visit 2 Treatment 1 Follow-up	Visit 3 Treatment 1 Follow-up, Treatment 2
Time Point	Day 1 (Day 0)	Day 7 ± 1 From Visit 1	Day 7 ± 1 from Visit 2
Estimated Visit Duration	2.5 hours	1.0 hours	1.5 hours
Compliance		x	x
Study Lens Wear Time		x	x
Follow-up PRO and CLDEQ-8 Questionnaire		x	x

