7.2. Detailed Study Procedures

VISIT 1

Subjects may report to the initial visit wearing their habitual contact lenses or spectacles (if required)

Visit 1: Screening			
Step	Procedure	Details	
1.1	Statement of Informed Consent	Each subject must read, understand, and sign the Statement of Informed Consent before being enrolled into the study. The Principal Investigator or his/her designee conducting the informed consent discussion must also sign the consent form. Note: The subject must be provided a signed copy of this document.	
1.2	Demographics	Record the subject's year of birth, age, gender, race and ethnicity.	
1.3	Medical History and Concomitant Medications	Questions regarding the subjects' medical history and concomitant medications.	
1.4	Current Habitual Correction	Record the subject's current habitual correct (i.e. Spectacles or Contact lenses)	
1.5	Habitual Lenses (if applicable)	Questions regarding the subject's habitual lens type and parameters.	
1.6	Contact Lens History (If applicable)	Record the subject's correction type (i.e. monovision, multifocal, sphere with readers, etc.).	
1.7	Wear time and Comfortable Wear time with Habitual lenses (If applicable)	Record the subjects wear time and comfortable wear time with their habitual contact lenses.	
1.8	Eligibility after Screening	All responses to Screening Inclusion Criteria questions must be answered "yes" and all responses to Exclusion Criteria must be answered "no" for the subject to be considered eligible. If subject is deemed to be ineligible after screening, proceed to Final Evaluation and complete Subject Disposition. Refraction and Biomicroscopy forms are not required.	

Visit 1: Baseline			
Step	Procedure	Details	

Visit 1: Baseline			
Step	Procedure	Details	
1.9	Ocular Symptoms	Subjects will respond to a verbal open-ended symptoms questionnaire.	
1.10	Entrance Distance and Near Visual Acuity	Distance and near Snellen visual acuity will be measured for each eye with the subject's habitual correction in place (if required). For near measures use the ETDRS 2000 Series Chart 1 or 2. The acuity will be recorded to the nearest letter OD, OS and OU.	
1.11	Lens Removal (If applicable)	Have the subject remove their habitual lenses and store in an approved storage solution.	
1.12	Keratometry	Keratometry will be performed OD and OS and the steep and flat dioptric power and corresponding meridians recorded.	

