1.31	Lens Power Modification (if applicable)	If the subject reports unsatisfactory vision, or is unable to obtain 20/30 distance visual acuity OU with the lenses than a modification must be attempted. If the subject reports satisfactory vision with the lenses a modification is not required however may at the Investigators discretion based upon their findings on the measured visual acuity and/or over- refraction.	

		
Select the reason(s) for lens change (select all that apply):
 
 • The settled lens rotation is such that one of the other available lens cylinder axis would be better (use LARS rule to determine the replacement lens cylinder axis) • Power Modification needed • Unsatisfactory Vision • Other (specify reason) 
If one or both lenses are modified, repeat steps 1.20 through 1.30 for one or both eyes as appropriate. A maximum of two lens modifications are allowed.
	
1.32	Post-Fit Questionnaire	The subject will evaluate the vision characteristics, comfort characteristics, handling characteristics, and visual symptoms of the study lenses using the PRO questionnaire.	
1.33	Insertion and Removal Training (I/R) (if applicable)	
Neophytes and / or lapsed wearers who the investigator determines I/R training is required will receive training on lens insertion, lens removal, lens care and general contact lens safety information.
 
Additional lenses may be used if necessary to complete the I&R training. Record the lens information on the Lens log and in EDC.
 
Note: Instruct the Neophytes / Lapsed wearer subjects to follow this wear schedule for the study lenses: Dispensing day: 6 hours of wear Day 1: 6-8 hours of wear Day 2: 6-10 hours of wear Day 3: 6-12 hours of wear Day 4 and subsequent days: 6 to all waking hours of wear
	
1.34	Determination of I/R Success (if applicable)	
The subject must be able to successfully insert and remove the contact lenses to be dispensed lenses and continue in the study.
 
Note: If the subject is not able to successfully insert and remove the contact lenses the subject will be discontinued. Remove the lenses and complete the Final Evaluation.
	

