14. STATISTICAL METHODS

14.1. General Considerations

All data summaries and statistical analyses will be performed using the SAS software Version 9.4 or higher (SAS Institute, Cary, NC). Throughout the analysis of data, the results for each subject/eye will be used when available for summarization and statistical analysis. Unscheduled visits will be summarized separately and will be excluded from the statistical analysis.

Summary tables (Descriptive statistics and/or frequency tables) will be provided for all baseline variables, efficacy variables and safety variables as appropriate. Continuous variables will be summarized with descriptive statistics (n, mean, standard deviation (SD), median, minimum and maximum). Frequency count and percentage of subjects or eyes within each category will be provided for categorical data.

Summaries will be presented by study lens type and will be performed separately by completion status. All analyses will be conducted on per-protocol population (see Section 14.3).

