14.2. Sample Size Justification

A total of approximately 40 eligible subjects will be enrolled into the study at this site. At least 36 subjects will complete this study.

Using the POWER procedure in SAS 9.4, below is the summary of sample size required based on the different assumptions of the true LogMAR visual acuity and CLUE scores. The sample size was calculated for the non-inferiority tests (using 0.05 as the margin) with at least 90% of statistical power and 2-sided type I error of 0.05. Assuming the true LogMAR visual acuity is between 0.00 to 0.05 (distance) or 0.08 to 0.12 (near), and true CLUE vision score is between 38 to 42 points.

- Binocular LogMAR visual acuity (distance)

True Value	Estimated Standard Deviation	# of subjects needed	Actual Power
0.00	0.12	18	0.915
0.02	0.12	26	0.904
0.05	0.12	63	0.902

- Binocular LogMAR visual acuity (near)

True Value	Estimated Standard Deviation	# of subjects needed	Actual Power
0.08	0.12	21	0.905
0.10	0.12	33	0.901
0.12	0.12	63	0.902

- CLUE vision score

True Value	Estimated Standard Deviation	# of subjects needed	Actual Power
38	17	87	0.902
40	17	50	0.903
42	17	33	0.906

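### The primary CLUE model must adjust for baseline values, but no visible step before lens fitting collects a CLUE or other subject-rated vision score

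*Combined protocol and SAP*

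**What the plan says.** Primary hypothesis 3 (Section 2.3) claims that the CLUE vision score after 12-16 days is better than 32 points and names the instrument: "This will be recorded by the subject using the CLUE follow-up questionnaire".

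For the analysis, Section 14.5 states: "CLUE vision scores will be analyzed using a linear mixed model adjusting for baseline values as fixed covariate". The response times in that model are 6-8 days and 12-16 days. Age, gender and add power may be added when judged appropriate; the baseline term carries no such qualifier. Success is declared if the lower 95% limit of the least-squares mean exceeds 32.

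Table 3 (Section 7.1) has two rows for patient-reported outcomes: "Post Fit Questionnaires", marked at Visits 1 and 2, and "Follow-up PRO and CLDEQ-8 Questionnaire", marked at Visits 2 and 3. Step 1.32 in Section 7.2 describes the first of these: "The subject will evaluate the vision characteristics, comfort characteristics, handling characteristics, and visual symptoms of the study lenses using the PRO questionnaire". Among the steps before fitting, step 1.9 reads: "Subjects will respond to a verbal open-ended symptoms questionnaire".

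Section 14.2 sizes the CLUE comparison on the assumption that the "true CLUE vision score is between 38 to 42 points", with SD 17. Section 14.1 adds: "All analyses will be conducted on per-protocol population".

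**The concern.** One of the three primary comparisons contains a compulsory term, and the procedures that can be read do not supply it. The analyst must drop the term, substitute the post-fit score, or use something else. Each choice can give a different interval to compare with 32, so the pass or fail decision depends on a choice that the plan leaves open. Section 14.10 asks only that a change be documented and justified in the study report. The study has one arm and site staff are not masked, so the choice should not be left until scores are visible.

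The most obvious substitute, the step 1.32 score, is not a baseline in the usual sense. It is an early rating of the lens under test.

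**Working it through.** **1. Looking for the baseline score.** Steps 1.1-1.19 precede lens selection and fitting. What they record:

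- Consent, demographics, medical history and medications (1.1-1.3).
- Habitual correction, habitual lenses, contact lens history, and wear and comfortable wear time (1.4-1.7).
- Eligibility (1.8, 1.19), which includes the presbyopic symptoms questionnaire where it applies.
- Open-ended ocular symptoms (1.9).
- Acuity, keratometry, refraction, add and dominance (1.10, 1.12-1.17), with lens removal at 1.11.
- Slit lamp (1.18).

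Several of these are answered by the subject, but none is scheduled as a CLUE or vision rating. Acuity is measured before fitting but is not a CLUE score. The first such questionnaire is step 1.32, after insertion, settling, fit assessment and up to two lens modifications.

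**2. What Section 14.2 sizes.** Inputs: threshold 32, SD 17, two-sided alpha 0.05, power at least 90%. A one-sample t-test with no covariate (noncentral t, noncentrality (true mean − 32)·√n/17) gives:

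| True mean | n in plan | Power in plan | Recomputed power at n | Power at n − 1 | Power at 36 |
|---|---|---|---|---|---|
| 38 | 87 | 0.902 | 0.9024 | 0.8990 | 0.54 |
| 40 | 50 | 0.903 | 0.9035 | 0.8975 | 0.78 |
| 42 | 33 | 0.906 | 0.9059 | 0.8967 | 0.93 |

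All three rows reproduce exactly, so the sample size is that of an unadjusted mean.

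**3. What a covariate does to the interval (conditional note).** Assume complete data, one continuous covariate, and the least-squares mean taken at the sample covariate mean. The least-squares mean then equals the raw mean. Its model standard error is about 17·√(1 − R²)/√n. For the population mean it is 17/√n, because the covariate mean itself varies from sample to sample. With n = 36:

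- Unadjusted half-width: 2.030 × 17/6 = 5.75.
- Adjusted half-width: 2.032 × 17·√(1 − R²)/6 = 5.46, 4.82 and 4.07 at R² = 0.1, 0.3 and 0.5.
- Ratio of unadjusted to adjusted: 1.05, 1.19 and 1.41.

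The documents give no R², so the values below are assumptions. The simulation used a true mean of 32 and 1,000,000 replicates per row:

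| R² | One-sided false success | Coverage of population mean | Coverage given observed covariates |
|---|---|---|---|
| 0 | 2.5% | 95.0% | 95.0% |
| 0.1 | 3.1% | 93.8% | 95.0% |
| 0.3 | 4.9% | 90.2% | 95.0% |
| 0.5 | 8.0% | 84.0% | 95.0% |

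Smaller separate runs gave false success of 3.0-3.1%, 4.9-5.0% and 7.8-8.0% at the three non-zero values. The unadjusted interval stayed at 2.5% throughout. A two-visit version (time plus baseline, unstructured covariance, assumed residual correlation 0.5, approximate degrees of freedom) gave 3.1%, 4.9% and 8.1%.

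**The case against.** The strongest reply is that the model can be run. Table 3 heads Visit 1 as screening, baseline and treatment, and the post-fit questionnaire is given there, so its score may be what the authors meant. On that reading one sentence naming the questionnaire and visit would close the gap. The reading is possible, but the text does not state it, and it makes the covariate a rating of the study lens itself.

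A second reply is that the questionnaires in Appendix A, the symptoms questionnaire in Appendix D and Figure 1 are not shown. Hypothesis 3 speaks of a follow-up form, which might hint at another form. This stands as a limit on confidence. Against it, a baseline form would need a visit step, and the schedule that is shown has none before fitting.

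Third, the interval argument depends on the target. An adjusted least-squares mean has a valid interval given the observed covariates, and Section 14.5 does not say which target it intends. Sizing with an unadjusted SD is a common simplification and does not by itself declare an estimand. This also stands, and it is why that argument is only a conditional note.

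A reader might infer three stronger things that the documents do not support:

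- That no baseline CLUE form exists. The unseen appendices prevent that conclusion.
- That the adjusted analysis is biased, or has an error rate of 8%. The estimate equals the raw mean in complete data, and the error rate depends on an R² that the plan does not give.
- That the logMAR model has the same defect. It has no baseline term.

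**Conclusion.** The concern holds for the baseline term. On the visible text, a compulsory covariate in a primary model either has no data or is an on-treatment rating of the lens being tested. This is more than a missing detail, because following the plan literally leads to one or the other. Confidence is limited by the material that is not shown.

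The effect on the interval is secondary and conditional. It needs a continuous covariate that predicts the score, a least-squares mean at the sample covariate mean, and the population mean as target. Under those conditions, with 36 subjects, one-sided false success rises from 2.5% to about 3%, 5% and 8% at assumed R² of 0.1, 0.3 and 0.5. At R² of 0 nothing changes.

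**What to change.** In Section 14.5, before database lock, delete the baseline term from the primary CLUE comparison. Base the decision against 32 on the 12-16 day mean from the repeated-measures model with time as the only fixed effect. The per-protocol set requires all visits to be completed, so with no missing scores this is the raw mean; under the unstructured covariance option its interval is the one-sample t interval that Section 14.2 sizes.

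Covariate-adjusted models can be reported as supportive, with the covariates named in advance and the questionnaire and visit that supply any baseline score stated. If the sponsor prefers to keep adjustment in the primary model, the source of the baseline score must be defined and the variance should include the sampling of the covariate mean. For one covariate with slope b and sample variance s², that means adding b²·s²/n to the model variance of the least-squares mean.

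The cost is wording only, with no new data. The primary interval is wider than the adjusted one by about 5%, 19% and 41% at R² of 0.1, 0.3 and 0.5, so any precision gain under the conditional reading is given up. Nothing is lost against the power in Section 14.2, which already uses the unadjusted SD of 17.

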14.6. Secondary Analysis

Not Applicable.

14.7. Other Exploratory Analyses

Not Applicable.

14.8. Interim Analysis

Not Applicable.

14.9. Procedure for Handling Missing Data and Drop-Outs

Missing or spurious values will not be imputed. The count of missing values will be included in the summary tables and listings.

Subject dropout is expected to be one of the main reasons of missing data in this clinical trial. Past clinical trials don't provide the evidence that subject dropout is systematic or not-at-random. To evaluate the impact of missing data, sensitivity analysis will be conducted using multiple imputation methods if the proportion of subject dropout is greater than the 15%. The SAS/STAT procedures PROC MI and PROC MIANALYZE will be utilized with a parametric regression method used to make at least 5 imputations.

14.10. Procedure for Reporting Deviations from Statistical Plan

The analysis will be conducted according to that specified in above sections. There are no known reasons for which it is planned to deviate from these analysis methods. If for any reason a change is made, the change will be documented in the study report along with a justification for the change.

15. DATA HANDLING AND RECORD KEEPING/ARCHIVING

15.1. Electronic Case Report Form/Data Collection

The data for this study will be captured on electronic case report forms (eCRFs) using an EDC system (Bioclinica). An authorized data originator will enter study data into the eCRFs using the EDC system. Data collected on equipment that is not captured in EDC will be formatted to the specification of the JJVC database manager and sent to JJVC for analysis

The clinical data will be recorded on dedicated eCRFs specifically designed to match the study procedures for each visit. Once completed, the eCRFs will be reviewed for accuracy and completeness and signed by the Investigator. The sponsor or sponsor's representatives will be authorized to gain access to the subject recordation for the purposes of monitoring and auditing the study.

Edit checks, electronic queries, and audit trails are built into the system to ensure accurate and complete data collection. Data will be transmitted from the clinical site to a secure central database as forms are completed or updated, ensuring information accuracy, security, and confidentiality. After the final database lock, the Investigator will be provided with Individual Patient Profiles (IPP) including the full audit trail on electronic media in PDF format for all of the study data. The IPP must be retained in the study files as a certified copy of the source data for the study.

The content and structure of the eCRFs are compliant with ISO14155:2011.¹

